8.1.3 Safety Analysis

Safety analyses will be carried out using the Safety Analysis Set. Treatment-emergent AEs and SAEs, will be summarized and reported. Treatment-emergent AEs for DB Treatment Period 1 are defined as reported AEs that have a start date either on or after the first dose of the study drug during DB Treatment Period 1 and up to the end of DB Treatment Period 1. For DB Treatment Period 2, treatment emergent AEs are defined as reported AEs that have a start date either on or after the first dose of study drug during DB Treatment Period 2 and up to the end of DB Treatment Period 2. Adverse Events that occur during the administration of OL Creon[®] will be summarized separately for events that happen during the screening period and after randomization. The number and percent of subjects experiencing AEs will be tabulated by system organ class (SOC) and Medical Dictionary for Drug Regulatory Activities (MedDRA®) preferred term. In addition, summary of AEs by severity and relationship to study drug will be presented. Serious AEs, or AEs that lead to premature study discontinuation will be listed and described in detail. All these summaries will be done by treatment group. Mean change in vital signs and laboratory variables at each visit will be summarized. The last evaluation prior to the first dose of DB study drug in the corresponding treatment period will be used as baseline for the analysis in that treatment period. A frequency table will be presented for Potentially Clinically Important (PCI) vital sign findings. Shift tables for laboratory variables will be presented according to the reference ranges (low, normal or high).

Due to the small number of subjects per treatment group, only summary statistics will be applied to all the safety parameters.

8.2 Determination of Sample Size

8.2.1 Non-inferiority Margin Justification

The selection of a non-inferiority margin of 12% for the CFA is based on historical placebo-controlled Creon[®] Study S245.3.126, which had a similar study design (two-period, two-sequence cross-over) as Study M16-111, and enrolled 31 CF subjects with confirmed EPI based on the eligibility criteria of a historical CFA < 70%, or current

or historical fecal elastase-1 < 50 μ g/g. The effect of Creon[®] compared to placebo in CFA was estimated as 39.02% (95% CI: 32.3% – 45.8%). However, it is expected that the current study will enroll subjects with more severe EPI than the subjects in Study S245.3.126, as the enrollment criteria for EPI in the current study is more stringent: subjects need to have a baseline fecal elastase less than 15 μ g/g to be enrolled. Therefore, the non-inferiority margin for comparing Pancrelipase DR MP to Creon[®] (Part 1) or comparing Pancrelipase DR AAPIS to Creon[®] (Part 2) should be derived based on Creon's effect in a more comparable subject population in the historical study. At the time of the writing of this amendment, all subjects enrolled in Study M16-111 had a screening FE-1 of less than 15 μ g/g and a screening CFA below 50%.

A subgroup analyses in Study S245.3.126 has been performed to estimate the Creon effect in subjects with a more severe EPI, defined as having a CFA of 50% or less during the placebo treatment period (since the screening FE-1 value was not collected in Study S245.3.126). The Creon effect compared to placebo in CFA was estimated as 52.25% (95% CI: 47.0% - 57.5%) in this subject population. Based on the lower bound of the 95% CI for the estimate of Creon effect, a non-inferiority margin of 12% would preserve over 70% of that effect ((47-12)/47=74%).

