5.6.3 Suitability of Subject Population

Patients aged 12 years or older with CF were selected for this study because they represent a commonly diagnosed and investigated population in terms of maldigestion and secondary malabsorption due to EPI. The clinical symptoms, the need for enzyme supplementation and the therapeutic objectives for treating maldigestion are well defined in these patients.

Patients with pancreatic insufficiency often have a variable dosing regimen highly dependent on food intake and pattern. Even though patients may be well controlled by their PERT prior to study participation, there is a risk that participation in the study with a diet that contains different amounts of fat and protein than their usual pre-study diet may

result in some gastrointestinal symptoms. However, considering the short duration of the study periods with study drug intake, and the fact that subjects will be carefully observed during confinement/hospitalization, and return immediately to their usual diet, and the fact that the PERT dose during confinement will be adjusted to the new fat content of the diet, the risk of destabilizing their underlying condition is considered minimal.

It has been previously shown that an inverse linear correlation exists between the level of the remaining endogenous lipase activity and the improvement in CFA induced by PERTs.⁷ The enrollment of subjects with low endogenous lipase activity (more severe disease) may improve the interpretability and clinical relevance of on-treatment CFA values in PERT trials.

Therefore, in order to select a more severe patient population, the most conservative cutoff for fecal elastase-1 of $< 15 \ \mu g/g$ was chosen to select subjects with EPI. Removing the requirement for a screening off-PERT CFA < 70% is particularly relevant, given the challenges elicited by the ongoing COVID-19 pandemic.

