8.2.3 Blinded Sample Size Re-Estimation (BSSR)

For Part 1, with a sample size of 22 evaluable subjects, the study Part is sufficiently powered if the SD of the within-subject treatment difference in CFA is 12%. For Part 2, with a sample size of 18 evaluable subjects, the study Part is sufficiently powered if the SD of the within-subject treatment difference in CFA is 10%. However, if the actual SD for a respective study Part is larger than the assumed SD (12% or 10% for Part 1 or Part 2, respectively), the power for that study Part may be insufficient. In order to ensure the assumption of SD holds for the study, a **blinded** review and estimate of the SD will be conducted for each study Part when the CFA data from the two treatment periods for approximately half of the planned subjects are available. If the estimate of the SD is much different from the assumed SD, the sample size of the study may be adjusted based

on the estimated SD from the blinded data. The detailed BSSR plan is documented in the SAP.

As of the date of the approval of protocol amendment 7, Part 1 BSSR has been completed. The blinded estimate of the SD for the within-subject treatment difference in CFA from Part 1 was approximately 7%. Per the BSSR plan specified in the SAP, the Part 1 sample size remains the same as 22 evaluable subjects. However, the assumption of the SD used in the Part 2 sample size determination has been adjusted to 10%.

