2.4 Sample Size Determination

The sample size determination consists of a power calculation for the total number of evaluable subjects needed and assumptions for percentage of drop-outs for the total number of subjects enrolled. A non-inferiority margin of 12% is chosen for the study. This non-inferiority margin for comparing Pancrelipase DR MP to Creon® (Part 1) or comparing Pancrelipase DR AAPIS to Creon® (Part 2) was derived based on Creon's effect in a more comparable subject population in the historical study with a similar study design as follows:

Based on historical data from 4 placebo-controlled studies (Studies S223.3.101¹, S223.3.102², S245.3.126³, S245.3.127⁴), the effect in CFA is 36.8% (95% confidence interval: 32.6% – 41.0%) comparing Pancrelipase DR Capsules 24,000 with placebo.

Specifically, in the historical placebo-controlled Creon® Study S245.3.126³, which had a similar study design as Study M16-111 (as a two-period, two-sequence cross-over study conducted in an adult population at the same dose strength as M16-111), the effect of Creon® compared to placebo in CFA was estimated as 39.02% (95% CI: 32.3% – 45.8%) based on 31 enrolled CF subjects with confirmed EPI based on the eligibility criteria of a historical CFA < 70%, or current or historical Fecal Elastase-1 (FE-1) < 50 μ g/g. However, it is expected that the current Study M16-111 will enroll subjects with more severe EPI than the subjects in Study S245.3.126, as the enrollment criteria for EPI in the current study is more stringent: subjects need to have a baseline FE-1 less than 15 μ g/g to be enrolled. At the time of the protocol amendment 6, all subjects enrolled (N=10) in Study M16-111 had a screening FE-1 of less than 15 μ g/g and a screening CFA below 50%.

A subgroup analysis in Study S245.3.126 was performed to estimate the Creon effect in subjects with a more severe EPI, defined as having a CFA of 50% or less during the placebo treatment period (since the screening FE-1 value was not collected in Study S245.3.126). The Creon effect compared to placebo in CFA was estimated as 52.25% (95% CI: 47.0% - 57.5%) in this subject population. Based on the lower bound of the 95% CI for the estimate of Creon effect, a non-inferiority margin of 12% would preserve over 70% of that effect ((47-12)/47=74%).

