4.0 Analysis Populations

The following population sets will be defined and used for the analyses for each study Part.

[figure not shown]
The Screening Confinement Set consists of all subjects who started screening confinement. The screening confinement period was removed from the study design in protocol amendment 6. Therefore, the Screening Confinement Set (denoted SC-P1) is only defined for Part 1 and includes subjects screened under protocol Amendment 5 or earlier.

The Intent-to-Treat (ITT) Population includes all randomized subjects in each study Part (denoted as ITT-P1 and ITT-P2 for Part 1 and Part 2, respectively). Subjects will be included in the analysis according to the treatment sequence to which they are randomized.

The Evaluable Set (ES) consists of all randomized subjects in each study Part who complete both double-blind (DB) treatment periods and have 100% of stool samples collected and analyzed by the laboratory and valid total fat intake value for both DB treatment periods. The ES for Part 1 and Part 2 will be denoted as ES-P1 and ES-P2, respectively. Subjects will be included in the analysis according to the study drug that they actually received.

The Safety Analysis Set consists of all randomized subjects who received at least 1 dose of study drug in the DB treatment periods in each study Part (denoted as SA-P1 and SA-P2 for Part 1 and Part 2, respectively). Subjects will be included in the analysis according to the regimen that they actually received.

The Open Label Safety Analysis Set in each study Part consists of all subjects who received at least 1 dose of open label Creon during any study period (denoted as OLSA-P1 and OLSA-P2 for Part 1 and Part 2, respectively). For Part 1, subjects who received open label Creon during the maintenance period (only applicable for subjects enrolled prior to protocol amendment 6) will also be included in OLSA-P1.

For Part 1, the population sets include: the Screening Confinement Set (SC-P1), Intent-to-Treat Population (ITT-P1), Evaluable Set (ES-P1), Safety Analysis Set (SA-P1) and Open Label Safety Analysis Set (OLSA-P1). For Part 2, the population sets include: the Intent-to-Treat Population (ITT-P2), Evaluable Set (ES-P2), Safety Analysis Set (SA-P2) and Open Label Safety Analysis Set (OLSA-P2).

[figure not shown]

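### Does the 12-point non-inferiority margin need a new justification because its 74% preservation figure comes from a subgroup selected on placebo-period CFA?

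*Protocol*

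**What the plan says.** Protocol 8.2.1 and SAP 2.4 (Sample Size Determination) follow the same argument.

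- **Full-study effect.** In S245.3.126, which enrolled 31 subjects, the Creon effect "compared to placebo in CFA was estimated as 39.02% (95% CI: 32.3" to 45.8). The SAP adds a pooled estimate from four placebo-controlled studies: 36.8, 95% CI 32.6 to 41.0.
- **Reason for a subgroup.** M16-111 requires FE-1 below 15 µg/g, so its subjects are expected to have more severe EPI than those in S245.3.126. Screening FE-1 was not collected in that study, so severity was "defined as having a CFA of 50% or less during the placebo treatment period". The effect in that subgroup was 52.25 (95% CI 47.0 to 57.5).
- **Claim.** On the lower bound of that interval, "a non-inferiority margin of 12% would preserve over 70% of that effect ((47-12)/47=74" percent.
- **Evidence that enrolled subjects match.** The Protocol, now at Amendment 7, says: "At the time of the writing of this amendment, all subjects enrolled in Study M16-111 had a screening FE-1 of less than 15" µg/g and a screening CFA below 50%. The SAP reports the same facts as "At the time of the protocol amendment 6, all subjects enrolled (N=10").
- **Source of the screening CFA.** SAP 4.0 says that the screening confinement was removed in Amendment 6 and that its analysis set "is only defined for Part 1 and includes subjects screened under protocol Amendment 5 or earlier". Protocol 5.6.3 refers to the dropped criterion: "Removing the requirement for a screening off-PERT CFA < 70% is particularly relevant".

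Protocol 8.1.2 compares the two-sided 99% CI for the mean CFA difference with this margin in each Part.

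**The concern.** The margin is the only decision threshold in either Part, and these two sections are its only justification. Three features invite doubt.

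First, the subgroup is defined by one of the two measurements that make up the effect. Subjects whose placebo-period CFA happened to be low are more likely to be included, and the same low value enlarges their Creon-minus-placebo difference. This regression to the mean biases both 52.25 and its lower bound upward. Without the subgroup size, a reader cannot judge how firm the bound is.

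Second, the bounds printed for unselected populations give a clearly lower preserved fraction, which neither document works out.

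Third, the only observed link between M16-111 subjects and the subgroup is screening CFA in 10 subjects. Subjects first screened under Amendment 6 or later have no screening CFA, yet the Protocol's wording makes the evidence look current at Amendment 7.

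If the enrolled subjects resembled the full S245.3.126 population more than the subgroup, the margin would concede a larger share of the Creon effect than the text suggests.

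**Working it through.** **1. The plan's own figure.** Preserved fraction = (L − M)/L, with L the lower 95% bound and M = 12.

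(47.0 − 12)/47.0 = 0.745, which reproduces the printed 74%.

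**2. The same formula on the other printed lower bounds.**

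| Source | L | (L − 12)/L |
|---|---|---|
| Subgroup, S245.3.126 | 47.0 | 74.5% |
| All S245.3.126 | 32.3 | 62.8% |
| Four studies pooled (SAP) | 32.6 | 63.2% |

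A preserved fraction of 70% needs L = 12/0.30 = 40.0. Half of the full-study bound is 16.15, so a 12-point margin still preserves more than half of it.

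**3. Selection bias (illustration only).** Under a normal model, bias = (e²/S) × φ(z_p)/p, where e is the period error SD, S the SD of placebo-period CFA, p the share of subjects selected, and z_p the normal quantile of p. The documents give neither S nor p. I assume S from 16 to 22 and p from 0.4 to 0.6. For e I take D/√2, with D the SD of the within-subject difference: 7 (Protocol 8.2.3: "The blinded estimate of the SD for the within-subject treatment difference in CFA from Part 1 was approximately 7" percent), and 10 and 12 (Protocol 8.2.2).

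Example with D = 10, S = 16, p = 0.4: e² = 50, φ(z_p) = 0.386, bias = (50/16) × (0.386/0.4) = 3.02. Then L = 43.98 and (43.98 − 12)/43.98 = 72.7%.

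| D | Bias (points) | Preserved fraction |
|---|---|---|
| 7 | 0.7 to 1.5 | 73.6% to 74.1% |
| 10 | 1.5 to 3.0 | 72.7% to 73.6% |
| 12 | 2.1 to 4.3 | 71.9% to 73.3% |

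These SDs describe on-enzyme periods, and placebo-period error may be larger. Reaching 70% in the worst cell (S = 16, p = 0.4) needs e of about 10.8.

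A rough upper check uses the full-study CI. Its half-width is (45.8 − 32.3)/2 = 6.75. If all 31 subjects were analysed, D = 6.75 × √31/2.04 ≈ 18.4, so e² ≈ 169. The bias is then 5.0 to 10.2 points, L is 36.8 to 42.1, and the preserved fraction is 67% to 71%. This overstates the error, because a placebo-versus-enzyme difference also varies through real differences between subjects in their response.

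**4. The decision rule.** The 99% CI half-width is t(0.995, N − 2) × SD/√N. At the blinded Part 1 SD of about 7 it is 2.845 × 7/√22 = 4.2 points for N = 22. If the same SD held in Part 2, it would be 2.921 × 7/√18 = 4.8 points for N = 18. The reported interval will let any reader judge the result against a margin tighter than 12.

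**5. The date.** SAP 2.4 ties the screening-CFA statement to Amendment 6 and 10 subjects. The Amendment 7 summary of changes lists no edit to 8.2.1. The Part 1 blinded re-estimation was planned at 13 subjects with CFA from both periods (SAP 2.4.1) and was complete by Amendment 7 (Protocol 8.2.3), so enrolment had very probably passed 10. Carried-over wording is the likely explanation. It is not proven, because later-enrolled subjects could have been screened under Amendment 5.

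**The case for a change.** The strongest case for a change is that a margin resting on one favourable number should carry its less favourable counterpart beside it. The bounds printed for unselected populations both give about 63%. FE-1 cannot link the two studies directly, since it was not collected at screening in S245.3.126. Ten subjects with screening CFA below 50% are thin evidence: 10 of 10 has an exact two-sided 95% lower limit of about 69% (0.025^(1/10) = 0.69). Printing the subgroup size and the 63%, and correcting the date, would cost a few words.

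Much of this is factually right. The subgroup size is missing, the direction of the bias is clear, and the Protocol and SAP date the same evidence differently. What does not stand is that the reader is misled or that the plan is weakened. Both documents print the full-study interval, the selection rule and the reason for it, and they confine the 70% claim to the subgroup effect. They also say openly that the margin depends on enrolling a more severe population. The missing 63% is one division on a number printed in the same section. SAP 7.1 already plans baseline summaries of FE-1 in both Parts and of screening-confinement CFA in Part 1, so the severity of the enrolled population will be reported beyond those 10 subjects.

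**Conclusion.** No change to the plan is needed. The 74% is correct for the effect it describes. The alternative is about 63%, a conservative reading because an FE-1 criterion below 15 µg/g plausibly selects more severe subjects than S245.3.126 enrolled. Neither document sets a required preserved fraction that 63% would fail. The selection bias is real in direction but cannot be sized from the documents. With the assumed S and p it leaves about 72% to 74% at the SDs the documents state, and about 67% to 71% under a deliberately pessimistic error SD. Every illustrated value lies between the two figures a reader can already derive.

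Nothing downstream depends on which figure is printed: the 12-point threshold, the 99% CI, the sample sizes and the planned analyses are the same either way. Adding the subgroup size and the lower figure is a reporting preference. The date mismatch between Protocol 8.2.1 and SAP 2.4 is most likely a clerical carry-over. The SAP already gives the more specific statement (Amendment 6, 10 subjects), so a reader of both documents can resolve it.

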8.2.2 Sample Size Determination

For each study Part, it is assumed that the expected difference in means of CFA between Creon[®] and Pancrelipase DR MP (Part 1) or between Creon[®] and Pancrelipase DR AAPIS (Part 2) is 0. For Part 1, with 22 subjects completing the 2 crossover treatment periods and having valid CFA in both periods, the power to claim non-inferiority is approximately 96% based on one-sided type I error of 0.005 (i.e., based on two-sided 99% CI for non-inferiority assessment), assuming a standard deviation (SD) of 12% for the within-subject treatment difference.

For Part 2, with 18 subjects completing the 2 crossover treatment periods and having valid CFA in both periods, the power to claim non-inferiority is approximately 98% based on one-sided type I error of 0.005 (i.e., based on two-sided 99% CI for non-inferiority

assessment), assuming a standard deviation (SD) of 10% for the within-subject treatment difference (see Section 8.2.3).

SD of Treatment Difference	Power (N=22)	Power (N=18)
8%	99%	99%
10%	99%	98%
12%	96%	89%
14%	87%	75%

Table 3.Study Power for Non-Inferiority in Primary Endpoint of CFA

Note: Power for non-inferiority in primary endpoint by evaluable sample size, if true CFA difference is 0.

It is expected that a screening failure rate of about 30% will be observed and that approximately 10-15% of the subjects will drop out during the crossover treatment periods. Based on these assumptions, approximately 36 subjects will be screened and approximately 26 subjects will be randomized in Part 1 to expect 22 subjects to complete the crossover treatment periods, and approximately 30 subjects will be screened and approximately 20 subjects will be randomized in Part 2 to expect 18 subjects to complete the crossover treatment periods.

8.2.3 Blinded Sample Size Re-Estimation (BSSR)

For Part 1, with a sample size of 22 evaluable subjects, the study Part is sufficiently powered if the SD of the within-subject treatment difference in CFA is 12%. For Part 2, with a sample size of 18 evaluable subjects, the study Part is sufficiently powered if the SD of the within-subject treatment difference in CFA is 10%. However, if the actual SD for a respective study Part is larger than the assumed SD (12% or 10% for Part 1 or Part 2, respectively), the power for that study Part may be insufficient. In order to ensure the assumption of SD holds for the study, a **blinded** review and estimate of the SD will be conducted for each study Part when the CFA data from the two treatment periods for approximately half of the planned subjects are available. If the estimate of the SD is much different from the assumed SD, the sample size of the study may be adjusted based

on the estimated SD from the blinded data. The detailed BSSR plan is documented in the SAP.

As of the date of the approval of protocol amendment 7, Part 1 BSSR has been completed. The blinded estimate of the SD for the within-subject treatment difference in CFA from Part 1 was approximately 7%. Per the BSSR plan specified in the SAP, the Part 1 sample size remains the same as 22 evaluable subjects. However, the assumption of the SD used in the Part 2 sample size determination has been adjusted to 10%.

8.3 Study Data Reporting

If one study Part (Part 1 or Part 2) is completed earlier than the other study Part, the database lock and formal unblinded analysis for the completed study Part will be performed. Analysis of one Part will not unblind the other. The AbbVie study team will review the efficacy and safety results from the unblinded analysis of the completed Part and an interim study report for the corresponding study Part may be prepared for regulatory submission.

8.4 Randomization Methods

For Part 1 at Visit 2 (DB Treatment Period 1 Day 1), eligible subjects will be randomized in a 1:1 ratio, to one of the 2 treatment sequence arms as shown below:

Treatment Period 1	Treatment Period 2		
Pancrelipase DR capsules MP	Creon [®] (Pancrelipase) DR capsules		
Creon [®] (Pancrelipase) DR capsules	Pancrelipase DR capsules MP		
	Treatment Period 1Pancrelipase DR capsules MPCreon [®] (Pancrelipase) DR capsules		

MP = modernized process uniform coated pellets, large scale

Subjects randomized to Sequence Arm A will take pancrelipase DR 24,000 MP drug product during DB Treatment Period 1 and then take Creon[®] during DB Treatment Period 2. Subjects randomized to Sequence Arm B will take Creon[®] during DB Treatment Period 1 and then take pancrelipase DR MP-drug product during DB Treatment Period 2.

For Part 2 at Visit 2 (DB Treatment Period 1 Day 1), eligible subjects will be randomized in a 1:1 ratio, to one of the 2 treatment sequence arms as shown below:

Sequence Arm	Treatment Period 1	Treatment Period 2		
С	Pancrelipase DR capsules AAPIS	Creon [®] (Pancrelipase) DR capsules		
D	Creon [®] (Pancrelipase) DR capsules	Pancrelipase DR AAPIS		

AAPIS = Delayed-release capsules of pancrelipase manufactured at an Alternate Active Pharmaceutical Ingredient Site; DR = Delayed release

Subjects randomized to Sequence Arm C will take Pancrelipase DR capsules AAPIS drug product during DB Treatment Period 1 and then take Creon[®] during DB Treatment Period 2. Subjects randomized to Sequence Arm B will take Creon[®] during DB Treatment Period 1 and then take Pancrelipase DR capsules AAPIS drug product during DB Treatment Period 2.

The randomization is central without any stratification. Randomization schedules for Part 1 and Part 2 are independent from each other. The randomization schedule will be prepared by the Randomization Personnel of AbbVie.

